4600 mg dose of VIS410 following viral challenge. Overall, 4600 mg VIS410 following pretreatment was generally well tolerated. None of the 4 subjects reported cramping or any other symptoms associated with severe infusion reactions. Mild and transient loose stools were observed in 3 of the subjects. A fourth subject had a transient episode of nausea and vomiting about 8.3 hours after the start of infusion. All events were considered resolved within 24 hours of onset.

Phase 1 (VIS410-102) Study VIS410-102 is a Phase 1, randomized, placebo-controlled study to evaluate safety, tolerability, and PK of a single 2300 mg and 3800 mg dose of VIS410 following administration of different pretreatment regimens. A total of 83 subjects received study drug (Placebo (n=12), VIS410 2300 mg (n=59), VIS410 3800 mg (n=12)). VIS410 2300 mg was evaluated at a 2-hour infusion (n=12), 4-hour infusion (n=12), 2-hour infusion following a pretreatment regimen of diphenhydramine 50 mg PO and ibuprofen 400 mg PO 60 minutes before infusion (n=12), 2-hour infusion following a pretreatment regimen of cetirizine 10 mg PO 60 minutes before infusion (n=12), and 2-hour infusion following a pretreatment regimen of diphenhydramine 50 mg PO and acetylsalicylic acid 325 mg PO 60 minutes before a 2-hour infusion (n=11). The 3800 mg VIS410 dose was evaluated at a 2-hour infusion following a pretreatment regimen of diphenhydramine 50 mg PO and ibuprofen 400 mg PO 60 minutes before infusion (n=12). The pretreatment regimens were selected in order to mitigate the GI AEs observed with VIS410. This study is currently ongoing and a preliminary summary of safety data to date is presented below.

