To date there have been no reports of SAEs. One subject at the 3800 mg dose discontinued study drug infusion due to AEs of nausea, vomiting, chills, and hot flashes. All events resolved after study drug discontinuation despite slow decrease in serum concentration of VIS410. VIS410 was not associated with any signs or symptoms that are consistent with systemic allergic reactions or anaphylaxis. Gastrointestinal events were observed at a higher frequency in the VIS410 treated subjects compared to Placebo. Based on the data from the 2300 mg and 3800 mg dose groups, VIS410 was associated with GI events ranging from mild to severe; however, a 2300 mg dose of VIS410 with a single-dose pretreatment regimen of diphenhydramine and low dose ibuprofen or acetylsalicylic acid was associated with a low rate of GI events (16.7% and 9.1%, respectively). Overall, the most commonly reported events were loose stool, diarrhea, and abdominal cramping. Subjects who received no pretreatment regimen had the highest number of GI AEs ranging from mild to severe. The prolonged infusion of VIS410 (over 4 hours) resulted in a larger number of GI events than the 2-hour infusion (41 events in 10 subjects vs. 18 events in 6 subjects, respectively), suggesting that GI events will not be mitigated by slowing the infusion rate. Pretreatment regimens of an antihistamine (cetirizine) or an antihistamine (diphenhydramine) plus a prostaglandin inhibitor (ibuprofen or acetylsalicylic acid) mitigated the GI events compared with the no pretreatment cohorts. The rate (13 GI events in 7 subjects) and severity of events (12/13 mild) were slightly lower in the cetirizine group than the no pretreatment groups. The lowest rate of GI events with VIS410 was observed in subjects who received the diphenhydramine plus acetylsalicylic acid pretreatment regimen, with only 1 subject reporting a mild episode of loose stool and abdominal pain approximately 22 hours after initiation of study drug administration that resolved spontaneously with no intervention. Another effective pretreatment regimen included diphenhydramine plus ibuprofen at both 2300 and 3800 mg

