dose, with only 2 subjects in the 2300 mg dose group reporting a mild episode of loose stool 7 to 9 hours after initiation of study drug administration that resolved spontaneously with no intervention and 1 report of mild nausea in the same subject. The same pretreatment with a higher dose of 3800 mg, showed a low rate of GI events with 1 subject reporting a mild episode of loose stool approximately 21 hours after start of infusion and another subject reporting mild nausea. Both events resolved spontaneously with no intervention. In addition, one (1) subject at the 3800 mg dose discontinued study drug infusion due to AEs of nausea, vomiting, chills, and hot flashes.

To date, no clinically significant changes have been observed in hematology, chemistry, and urinalysis parameters. Specifically, no alterations in electrolytes were observed in the subjects with loose stool or diarrhea.

In summary, the type and timing of GI AEs observed in this study are consistent with prior studies, are mostly mild in intensity, are self-limiting in nature, and resolve following the completion of infusion with no sequelae. These data suggest that a pretreatment regimen is necessary to mitigate the GI events associated with VIS410; however, an antihistamine alone may not be as effective in mitigating the AEs. Addition of a prostaglandin inhibitor/non-steroidal anti-inflammatory drugs (NSAIDs) such as ibuprofen or acetylsalicylic acid to an antihistamine was necessary to further reduce the frequency and severity of GI events. These data were consistent with previous safety data in an influenza virus challenge study where a regimen of diphenhydramine and ibuprofen mitigated the severity and or frequency of GI AEs in 8 subjects given 2300 mg (n=4) and 4600 mg of VIS410 (n=4).

For more detailed information on VIS410, refer to the current Investigator Brochure [5].

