3. STUDY ENDPOINTS

3.1 PRIMARY ENDPOINTS

- The proportion of subjects with adverse events (AEs) and serious adverse events (SAEs) following administration of VIS410
- The proportion of subjects with treatment-emergent AEs (TEAEs) including hypersensitivity reaction, anaphylactic reaction, and AEs of special interest (AESIs) following dosing

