4. STUDY DESIGN

4.1 OVERVIEW OF STUDY DESIGN

This is a Phase 2a randomized, double-blind, placebo-controlled study to be conducted in approximately 150 subjects with uncomplicated influenza. This study will include approximately 50–75 clinical sites worldwide.

Subjects will be admitted to an infusion unit for drug administration and observation following infusion. The study is designed to compare an infusion of a single high or low IV

[figure not shown]
dose of VIS410 against placebo. Subjects will be assigned randomly to receive VIS410 at a dose of 2000 mg (low dose) or 4000 mg (high dose) or placebo (0.9% sodium chloride) at a ratio of 1:1:1 using a permuted block randomization method. Eligible subjects will receive VIS410 2000 mg, VIS410 4000 mg, or placebo administered as a single IV infusion over 2 hours on Day 1. Subjects will receive a pretreatment regimen of diphenhydramine 50 mg PO and ibuprofen 400 mg PO or acetylsalicylic acid 325 mg PO 60 minutes before infusion.

The subjects will be observed for at least 2 hours after the end of the infusion and will have a follow-up phone call in the evening of the dosing day to ensure subjects' safety and well-being. Subjects will return for follow-up visits on Days 3 (± 1 day), 5 (± 1 day), 7 (± 1 day), 14 (± 3 days), 28 (± 3 days), 56 (± 7 days) and 100 (± 7 days). In addition, between clinic visits up to Day 7 (e.g., Days 2, 4 and 6) subjects will receive a follow-up telephone call to ensure compliance with FluPRO Influenza Symptom Questionnaire and review any new or worsening signs or symptoms. The Schedule of Assessments is presented in Table 1.

An independent Data Safety Monitoring Board (DSMB) will be established to review all available safety data after 30 subjects have completed the Day 5 visit and again after 75 subjects have completed the Day 28 visit. In addition, following the first DSMB, the DSMB will convene if the overall relative GI adverse event rate reaches 50% or the rate of moderate GI adverse events reaches 25%.

A schematic overview of the study design is shown in Figure 1. The assessments performed are summarized per visit in the Time and Events Schedule.

Figure 1. Schematic Overview of the Study

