An AESI (serious or non-serious) is one of scientific and medical concern specific to the Sponsor's product or program, for which ongoing monitoring and rapid communication by the Investigator to the Sponsor will be warranted. Such an event might warrant further investigation in order to characterize and understand it. Depending on the nature of the event, rapid communication by the trial Sponsor to other parties (e.g., regulators) might also be warranted (based on CIOMS VI).

For VIS410, the AESIs include the following:

- Abdominal cramping
- Diarrhea
- Nausea and vomiting
- Pruritus
- Rash

- Hypotension
- Throat tightening
- Trouble breathing or wheezing

Serious Adverse Event

An SAE is any untoward medical occurrence that at any dose meets any of the following conditions:

- results in death
- is life-threatening, i.e., the patient was at risk of death at the time of the event (e.g., ventricular fibrillation and anaphylaxis). The term does not refer to an event which hypothetically might have caused death if it were more severe.
- requires inpatient hospitalization or prolongation of existing inpatient hospitalization: Hospitalization refers to an overnight admission into hospital for the purpose of investigating and/or treating the AE. Hospitalization for an elective procedure, or routinely scheduled treatment for a pre-existing condition that has not worsened, is not an SAE.
- results in persistent or significant disability/incapacity, i.e., causing substantial disruption of the patient's ability to conduct normal life
- is a congenital anomaly/birth defect
- is medically significant, i.e., may not be immediately life-threatening or result in death or hospitalization but may jeopardize the patient's health or may require intervention to prevent one of the above outcomes. Examples of such events are intensive treatment in an emergency room or at home for allergic bronchospasm, blood dyscrasias, or convulsions that do not result in hospitalization or development of drug dependency or drug abuse.

Unlisted (Unexpected) Adverse Event

An AE is considered unlisted if the nature or severity is not consistent with the applicable product reference safety information (Investigator Brochure [5]).

Suspected Unexpected Serious Adverse Reactions

Suspected unexpected serious adverse reactions (SUSARs) are SAEs that are unexpected and judged by the Investigator or Sponsor to be related to the study treatment administered.

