12.1 Adverse Events

A TEAE is defined as an adverse event that starts on or after the date of study drug IV infusion. AEs that start on the day of infusion will be classified as TEAEs if the "Same day as infusion" question is answered as "Started after the infusion." All AEs will be coded using MedDRA version 19.1.

An overall summary of AEs and TEAEs will be presented by treatment group, including the combined low-dose and high-dose VIS410, and overall subjects, with subject counts, percentages, and the exact 95% CI for the percentage of subjects with the event. This summary will include subjects with any AE, any treatment-related AE, any TEAE, any treatment-related TEAE, any serious TEAE, any treatment-related serious TEAE, any TEAE of special interest (AESI), hypersensitivity reaction, anaphylactic reaction, any injection site AE, TEAEs by intensity, any moderate TEAE, any severe TEAE, TEAEs leading to study infusion discontinuation, treatment-related TEAEs leading to study infusion discontinuation, TEAEs leading to death, and treatment-related TEAEs leading to death.

TEAE definitions:

- All AESIs will be defined by the eCRF field event type - AESI
- Injection site AEs will be defined by the eCRF field event type - injection site AE
- Treatment related AEs will be defined by the investigators determination of the relationship as a reasonable possibility.
- Hypersensitivity and anaphylaxis reactions will be defined by clinical evaluation of TEAEs per the Safety Plan
- TEAEs leading to study infusion discontinuation will be defined by an answer of permanently discontinued as the eCRF action taken for an AE during infusion.

This summary will also be presented by region: US, Africa, Rest of the World.

A summary table by treatment group will present the number and percentage of subjects with TEAEs by SOC and SOC/PT. Subjects with multiple TEAEs within an SOC or SOC/PT combination will be counted only once for that SOC or SOC/PT combination. This table will also present a summary of subjects with any TEAE.

Similar summaries will be presented for Serious TEAEs, AESIs, injection site TEAEs, treatment-related TEAEs, TEAEs leading to study infusion discontinuation and TEAEs leading to death. The TEAE definitions for these tables will be the same as used in the overall summary of TEAEs.

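### The AESI list omits loose stool, so the primary AESI proportion could undercount VIS410's known gastrointestinal toxicity

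*Protocol*

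**What the plan says.** Protocol 3.1 makes AESIs part of a primary endpoint, the proportion of subjects with TEAEs including "hypersensitivity reaction, anaphylactic reaction, and AEs of special interest (AESIs) following dosing". Protocol 9.3.8 plans between-group differences in that proportion with 95% CIs.

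The list in Protocol 10.1 begins "For VIS410, the AESIs include the following" and has eight items. Three are gastrointestinal: abdominal cramping, diarrhea, and a joint item for nausea and vomiting. Loose stool is not among the eight.

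SAP 12.1 gives the counting rule: "All AESIs will be defined by the eCRF field event type - AESI". It supplies no preferred-term list. The Safety Plan it cites is used only for hypersensitivity and anaphylaxis.

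Protocol 1.3 says of VIS410-102: "Overall, the most commonly reported events were loose stool, diarrhea, and abdominal cramping". This trial's pretreatment, in Protocol 4.1, is "diphenhydramine 50 mg PO and ibuprofen 400 mg PO or acetylsalicylic acid 325 mg PO 60 minutes before infusion".

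**The concern.** The AESI proportion is the primary component meant to isolate toxicity specific to VIS410. The any-TEAE proportion does that poorly: in VIS-C001 it was 66.7% on VIS410 and 63.6% on placebo, although every diarrhea or loose-stool event was in a VIS410 subject.

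Under pretreatment of the kind used here, the narratives describe the GI toxicity mostly as loose stool, and no event in those groups is labelled diarrhea. If a site takes the list literally and does not flag loose stool, the SAP has no step that recovers the event. The loss would fall mainly on the active arms, shrink the difference from placebo and make VIS410 look better tolerated. With about 150 subjects at 50 to 75 sites, each site enrols on average 150/75 = 2 to 150/50 = 3 subjects, so uneven flagging is likely without a stated rule.

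**Working it through.** **Reproducing the protocol's own figures.** For VIS410-102 at 2300 mg, the two pretreatment regimens (ibuprofen, acetylsalicylic acid) are "associated with a low rate of GI events (16.7% and 9.1%, respectively"). The narratives give 2 affected of 12 and 1 of 11: 2/12 = 16.7% and 1/11 = 9.1%. Both match, so the narratives can be read as subject counts.

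**Inputs (Protocol 1.3 unless stated).** All groups had diphenhydramine plus the drug shown.

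| Study, dose, added drug | n | Subjects with GI events |
|---|---|---|
| VIS410-102, 2300 mg, ibuprofen 400 mg | 12 | 1 loose stool; 1 loose stool + nausea |
| VIS410-102, 2300 mg, acetylsalicylic acid 325 mg | 11 | 1 loose stool + abdominal pain |
| VIS410-102, 3800 mg, ibuprofen 400 mg | 12 | 1 loose stool; 1 nausea; 1 nausea + vomiting |
| VIS410-201, 2300 mg, ibuprofen 600 mg | 4 | 1 loose stool |
| VIS410-201, 4600 mg, same regimen carried forward | 4 | 3 loose stool; 1 nausea + vomiting |

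The 3800 mg loose-stool case is "1 subject reporting a mild episode of loose stool approximately 21 hours after start of infusion". The subject who stopped the 3800 mg infusion is taken as distinct from the one with mild nausea. For 4600 mg, Section 1.3 says "Mild and transient loose stools were observed in 3 of the subjects", whereas Section 1.5 gives loose stool in 2 of 4 and nausea and vomiting in 1. Section 1.5 does not make clear whether that subject was one of the two.

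**Which event is commonest.** VIS410-102: loose stool 1 + 1 + 1 + 1 = 4 of 35, nausea 3. Pooled: loose stool 4 + 1 + 3 = 8 of 43 (7 with the Section 1.5 count), nausea 4.

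**Share missed.** Let x be the subjects with loose stool and no listed GI event, and g all subjects with a GI event. The share is x/g. The exact (Clopper-Pearson) 95% limits are the 0.025 quantile of Beta(x, g−x+1) and the 0.975 quantile of Beta(x+1, g−x). Nausea alone is counted as listed. The two columns differ in whether abdominal pain counts as cramping.

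| Data | g | Pain counted | Pain not counted |
|---|---|---|---|
| VIS410-102 | 6 of 35 | 2/6 = 33% (4–78%) | 3/6 = 50% (12–88%) |
| Pooled, Section 1.3 counts | 11 of 43 | 6/11 = 55% (23–83%) | 7/11 = 64% (31–89%) |
| Pooled, Section 1.5, vomiting in a third subject | 10 of 43 | 5/10 = 50% (19–81%) | 6/10 = 60% (26–88%) |
| Pooled, Section 1.5, vomiting in a loose-stool subject | 9 of 43 | 4/9 = 44% (14–79%) | 5/9 = 56% (21–86%) |

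If the joint item is read as needing both nausea and vomiting, x rises by one in every cell: 3/6 to 4/6 in VIS410-102, and up to 8/11 = 73% pooled. These CIs also span 50%. On that reading the 3800 mg subject with nausea alone stays off the list even after loose stool is added.

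**Effect of adding loose stool (nausea alone counted).** VIS410-102: from 4/35 = 11.4% (or 3/35 = 8.6% if pain is not cramping) to 6/35 = 17.1%. Pooled on Section 1.3 counts: from 5/43 = 11.6% (or 4/43 = 9.3%) to 11/43 = 25.6%.

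**The case against.** The strongest reply is that sites may record loose stool as the AESI of diarrhea anyway.

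- **Grading.** A reader might infer that a single loose stool falls below Grade 1 diarrhea, because the Appendix 2 cell gives a count of 3–4 a day. But the cell also admits a mild or transient event, and Protocol 10.2 says semicolons in the grade descriptions mean *or*. A single mild episode can be read either way.
- **Terminology.** A reader might infer that the protocol always keeps the two terms apart. It does not: several passages in 1.3, 1.5 and 1.5.1 pair them, and 1.5 gives the pair one grade.
- **The list.** It is introduced by *include* and follows a general definition, so it is not stated to be closed. The eCRF guideline is not in the documents and may settle the matter, so it cannot be said that sites have nothing else to go on.
- **Other routes.** Loose stool still enters the AE and TEAE proportions, also primary, and the tables by preferred term, intensity and relationship. The DSMB trigger in 5.6 uses the overall GI event rate, not AESIs.

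All of this stands, and it limits the consequence. It does not remove the gap. Two permissible readings, no stated rule and a count taken only from the flag leave this component without a reproducible definition in the protocol or SAP. The TEAE tables would show a GI excess, but they would not correct the AESI comparison.

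**Conclusion.** The concern holds in limited form. The AESI list omits the commonest GI event seen under this kind of pretreatment, and the counting rule cannot recover what a site does not flag. If sites do not flag loose stool, the AESI proportion could miss roughly a third to two thirds of subjects with a GI event.

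A reader might infer that over half would be missed. The documents do not support that as a firm figure. VIS410-102, which used this trial's regimens, gives 2 or 3 of 6. The share passes half there only if abdominal pain is not cramping and the joint item also needs both nausea and vomiting. The pooled 6 or 7 of 11 relies on VIS410-201, where the ibuprofen dose was 600 mg, and on the Section 1.3 count for 4600 mg.

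The estimate assumes that no site flags loose stool, that narrative terms stand in for recorded terms, and that preliminary VIS410-102 data carry over to infected patients. The expected direction, towards better apparent tolerability, rests on loose stool occurring mainly on VIS410, as in VIS-C001. This is worth correcting, but the events are not lost to the trial.

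**What to change.** 1. In Protocol 10.1, change *Diarrhea* to *Diarrhea or loose stool*, and *Nausea and vomiting* to *Nausea and/or vomiting*. Extending *Abdominal cramping* to pain or discomfort is optional, since it rests on one subject.
2. Use the same terms for the AESI event type in the eCRF and its guideline.
3. In SAP 12.1, count AESIs from a prespecified term list alongside the site flag, fixed before unblinding.
4. Reconcile the 4600 mg loose-stool counts in Protocol 1.3 (3 of 4) and 1.5 (2 of 4).

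The cost is wording in the protocol, eCRF and SAP, with no added visits, samples or subjects. The downside is a somewhat higher reported AESI rate and more AESI reports for sites and sponsor to handle, some of them for a single mild episode.

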10.2 INTENSITY OF ADVERSE EVENTS

Each AE must be rated on a 3-point scale of increasing intensity according to DMID (Appendix 2):

Note: the semi-colon within the description of the grade indicates ‘or’.

- Grade 1 Mild transient or mild discomfort (<48 hours); no medical intervention/therapy required
- Grade 2 Moderate/mild to moderate limitation in activity—some assistance may be needed; no or minimal medical intervention/therapy required
- Grade 3 Severe/marked limitation in activity, some assistance usually required; medical intervention/therapy required, hospitalizations possible

10.3 CAUSALITY ASSESSMENT

The following binary choice will be used by the Investigator to describe the causality assessment with the test treatment:

Reasonable Possibility

There is evidence to suggest a causal relationship between the test treatment and the AE (e.g., AE is uncommon and known to be strongly associated with drug exposure or is uncommon in the study population, but not commonly associated with drug exposure).

No Reasonable Possibility

There is no evidence to suggest a causal relationship between the test treatment and the AE.

10.4 ACTION TAKEN REGARDING INVESTIGATIONAL PRODUCT

The action taken towards the study drug must be described as follows:

- Permanently discontinued
- Stopped temporarily
- Modified infusion rate
- No action Taken
- Not applicable

10.5 OUTCOME

The outcome of each AE must be rated as follows:

- Recovered/resolved
- Recovering/resolving
- Not recovered/not resolved
- Recovered with sequelae/resolved with sequelae
- Fatal
- Unknown

10.6 RECORDING OF ADVERSE EVENTS

All (S)AEs occurring during the clinical investigation must be documented in the EDC system.

Whenever possible, diagnoses should be given when signs and symptoms are due to a common etiology (e.g., skin erythema, induration, edema and warmth should be reported as “cellulitis”). Investigators must record their opinion concerning the relationship of the (S)AE to the study drug in the EDC system. All measures required for (S)AE management must be recorded in the source documents and reported according to Sponsor’s instructions.

All (S)AEs occurring at any time during the study (including the follow-up period) will be followed by the Investigator until satisfactory resolution (e.g., value back to baseline value) or stabilization or until final database lock. If necessary, in order to obtain additional information to ensure safety to the subject, additional blood and urine samples may be taken at the discretion of the Investigator. Certain long-term AEs related to therapy cannot be followed until resolution within the setting of this study. In these cases follow up will be the responsibility of the treating physician.

